1. SUMMARY OF THE PROTOCOL

EPA-AS POST-AUTHORIZATION OBSERVATIONAL STUDY

1.2. Methodological aspects

medical product of interest Not applicable
First ethics committee to evaluate the study: Autonomous CEIm of Galicia
Principal Investigators / Coordinators [REDACTED] [REDACTED]

[REDACTED]
 
[REDACTED]
 
[REDACTED]

Researcher/Coordinator Centers:
 
¹ Valencian Institute of Oncology
 
² San Carlos Clinical Hospital of Madrid
 
³ Puerta del Hierro-Majadahonda University Hospital
 
⁴ Lucus Augusti University Hospital, Lugo

Autonomous Communities of Researchers / Coordinators:
 
Valencian Community
 
Autonomous Community of Madrid
 
Galicia

Territorial scope:
 
National, Spain

Information source:
 
Medical records of the patients included after signing informed consent.
 
RETROSPECTIVE PART ONLY: medical records of patients included after signing informed consent or waiver thereof in the cases contemplated (see 6.3 Informed consent).

Type of study (according to the AEMPS classification):
 
EPA-AS

Tracking Type::
 
Ambispective (Prospective and retrospective). A 6-month follow-up is proposed for patients in the prospective part.

Total number of patients expected to include:
 
They are expected to include 250, sufficient to respond to the objectives set by the study.

Planned duration of the study:
 
Data collection 8 months. The estimated duration of the project is 12 to 18 months, depending on the patient inclusion rate.

Study duration for each participant:
 
No specific study visits will be carried out, other than obtaining informed consent in cases where it is required.

Main objectives:
 
a) Main objectives
 
i) Describe the population infected by COVID-19 with genitourinary tumors (urothelial cancer, prostate cancer, testicular cancer and renal cancer) treated in Spanish hospitals, know the clinical presentation, therapeutic evolution and

- prognosis of said intercurrent infectious process, as well as its possible relationship with different clinical and therapeutic factors.
- ii) Assess the possible relationship of the different oncological treatments administered to these patients with the clinical evolution of COVID-19 infection, considering both patients who have undergone oncological treatment previously, during or after COVID-19 infection.
- iii) To specifically evaluate the impact of COVID-19 infection on the toxicity of immunotherapy treatment (mainly pneumonitis) and the impact of immunotherapy on the evolution of the infectious condition in patients with tumors of genitourinary origin, in three different scenarios: during treatment, after treatment and in patients who are prescribed treatment after the infection has passed.
- iv) Analysis of this same relationship in patients with genitourinary tumors and asymptomatic COVID-19 infection with positive Ab serologies (IgM and IgG).
- v) To evaluate in patients with Prostate Cancer (PCa) the impact of androgen deprivation therapy (ADT) and new antiandrogen agents (NAH) with or without corticosteroids on infection. COVID-19.

b) Secondary objectives

- i) To evaluate the mortality associated with COVID-19 infection in the population with genitourinary tumors. Percentage of patients alive/dead at discharge.
- ii) To evaluate the rate (percentage) of complications that have required hospital admission and/or ICU treatment.
- iii) Describe the frequency of asymptomatic or minimally symptomatic COVID-19 infections. Percentage of asymptomatic patients or with mild symptoms included in the study.
- iv) Evolution of the oncological disease. Impact/influence of COVID-19 infection on the effectiveness of oncological treatment. Data will be collected on delays/modifications in follow-up or oncological treatment regimens. The average delay time and the number of modifications will be evaluated. Likewise, it is expected to obtain data on time to progression and overall survival of cancer patients, which can be compared with the reference values for each type of tumor pathology.

Main variables to evaluate (see section 5 of this protocol for more detail):

1. Epidemiological
2. Medical history
3. Tumor pathology
4. Immunotherapy treatment
5. Current oncological treatment
6. COVID-19 infection

Number of researchers:

32 centers

Scope of application:

Spain

2. INTRODUCTION AND JUSTIFICATION OF THE STUDY

2.1. Justification

We are immersed in a very rapidly evolving pandemic that puts patients from vulnerable populations, such as those diagnosed with cancer, at significant risk. Clinical data on COVID-19 in cancer patients is limited and new information is published with each passing day.

Without a doubt, a more accurate understanding of these risks will take us more time and, for now, the only thing we can do is educate the oncology population to minimize the risks of infection and to seek healthcare in case of suspicious symptoms.

Currently available information suggests that cancer patients are at higher risk of infections, serious complications, and more rapid deterioration from COVID-19 than other patients.⁽¹⁾ However, for now we do not have information on the complications associated with COVID-19 infection and the systemic treatments used in these patients.

It is known that chemotherapy causes a state of immunosuppression in cancer patients, associated or not with hematological toxicity secondary to most chemotherapy treatments. The more or less pronounced neutropenia that occurs after the administration of different chemotherapy regimens could be a factor that is related to a greater susceptibility to COVID-19 infection as well as a higher rate of complications. It could also be that the frequency of complications was lower because the immunological storm described during the virus infection did not occur, as the patient did not have a fully competent immune system.

Many patients with prostate cancer receive treatment with low-dose corticosteroids, with the intention of minimizing the toxicity associated with them. Corticosteroids have a hormonal, anti-inflammatory and regulatory role in patients' immunity. We also do not know to what extent these prolonged treatments may be related to a greater predisposition to COVID-19 virus infection, the development of complications or a more aggressive evolution of the disease.

Some organ toxicities secondary to immunotherapy oncology treatments may overlap with COVID-19 complications (e.g. pneumonitis, which causes 35% of toxic deaths caused by immunotherapy), so it may be difficult to distinguish whether they are an adverse effect of immunotherapy, a complication of COVID-19 infection, or a combination of both. Furthermore, a subgroup of patients with severe COVID-19 infection could suffer a "cytokine storm" syndrome, with elevated levels of IL-6, IFN- γ and other cytokines, similar to secondary hemophagocytic lymphohistiocytosis (sHLH), induced, although infrequently, due to viral infections^(2,3). In this scenario, the possibility of an immunological hyperreaction due to immunotherapeutic agents and a possible synergy between both mechanisms must also be considered. This could mean a higher rate of patients with complications from the viral infection. On the contrary, immunotherapy treatments could have a modulating effect on the immune response and, to a certain extent, protect against the "cytokine storm" condition, which is the one most closely related to serious complications due to virus infection.

Treatments with antiangiogenic tyrosine kinase inhibitors (TKIs), widely used in patients with kidney cancer, also have a role in regulating immunity, so it is also interesting to know what happens in these patients if they acquire the infection. coronavirus

2.2. Background and current situation

On December 31, 2019, the Wuhan Municipal Health and Sanitation Commission (Hubei Province, China) reported a cluster of 27 cases of pneumonia of unknown etiology, with common exposure to a seafood, fish, and animal wholesale market. alive in Wuhan city, including seven serious cases. The onset of symptoms in the first case was on December 8, 2019. On January 7, 2020, the Chinese

authorities identified a new type of virus from the Coronaviridae family as the causative agent of the outbreak, which has subsequently been named SARS-CoV-2, whose genetic sequence was shared by the Chinese authorities on January 12. On March 11, the WHO declared a global pandemic.

Coronaviruses are a family of viruses that cause infection in humans and a variety of animals, including birds and mammals such as camels, cats and bats. It is a zoonotic disease, meaning it can be transmitted from animals to humans.⁽⁴⁾. Coronaviruses that affect humans (HCoV) can produce clinical symptoms that range from the common cold with a seasonal pattern in winter to other more serious ones such as those produced by the Severe Acute Respiratory Syndrome (SARS) and of Middle East Respiratory Syndrome (MERS-CoV)⁽⁵⁾. Specifically, SARS in 2003 caused more than 8,000 cases in 27 countries and a fatality rate of 10% and since then it has not been detected in humans again. Since 2012, 2,499 cases of MERS-CoV have been reported in 27 countries (although the majority of cases have been detected in Saudi Arabia), with a fatality rate of 34%.

2.2.1. Epidemiological aspects of the infection

As in other outbreaks caused by coronaviruses, the most likely primary source of the disease caused by SARS-CoV-2 is animal origin. At this time it seems clear that the reservoir of the virus is the bat, while research continues on the intermediate host animal, with controversy between the pangolin and others. How the virus could have been transmitted from the animal source to the first human cases is unknown. Everything points to direct contact with infected animals or their secretions. In studies carried out in animal models with other coronaviruses, tropism has been observed for the cells of different organs and systems, mainly producing respiratory and gastrointestinal symptoms.⁽⁶⁾, which could indicate that transmission from the animal to humans could be through respiratory secretions and/or material from the digestive system. The route of transmission between humans is considered similar to that described for other coronaviruses through the secretions of infected people, mainly through direct contact with respiratory droplets of more than 5 microns (capable of being transmitted over distances of up to 2 meters) and hands or fomites contaminated with these secretions followed by contact with the mucosa of the mouth, nose or eyes⁽⁷⁾. SARS-CoV-2 has been detected in nasopharyngeal secretions, including saliva.

2.2.2. Clinic associated with COVID-19 infection

In the longest series published by the China Center for Disease Control, describing the characteristics of all cases detected in mainland China from the beginning of the outbreak to February 11, 2020 (72,314 cases), 1.2% of cases were asymptomatic⁽⁸⁾. These cases were detected in the context of exhaustive searches in intrafamilial outbreaks⁽⁹⁾ and some ended up developing symptoms⁽¹⁰⁾. In contrast, on the Diamond Princess ship, quarantined in Japan, where diagnostic tests were carried out on 3,700 passengers, 50% of those who had positive results were asymptomatic.^(11,12). Subsequently, after 14 days of observation, the majority developed symptoms, with the percentage of truly asymptomatic being 18% (95% CI: 15.5-20.2). Asymptomatic cases are more frequent in children and it has been observed that some of them present pulmonary radiological alterations, such as multifocal opacities and analytical alterations, such as elevated phosphatase.

The report of the WHO mission to China describes the most common symptoms and signs of 55,924 laboratory-confirmed cases, including: fever (87.9%), dry cough (67.7%), asthenia (38.1%), expectoration (33.4%), dyspnea (18.6%), sore throat (13.9%), headache (13.6%), myalgia or

arthralgia (14.8%), chills (11.4%), nausea or vomiting (5%), nasal congestion (4.8%), diarrhea (3.7%), hemoptysis (0.9%), and conjunctival congestion (0.8%)⁽¹³⁾. In Europe, with 14,011 confirmed cases reported to the European Surveillance System (TESSy) by 13 countries (97% of Germany), the most frequent symptoms were: fever (47%), dry or productive cough (25%), sore throat (16%), asthenia (6%) and pain (5%). In Spain, with 18,609 reported cases, the most frequent

Características clínicas	Yang (n=52) *	Chen (n=99)	Wang (n=138)	Guan (n=1099)
	%	%	%	%
Signos y síntomas				
Fiebre al ingreso	98,0	83,0	98,6	43,1
Tos	77,0	82,0	59,4	67,8
Astenia/Malestar	35,0	ND	69,6	38,1
Anorexia	ND	ND	39,9	ND
Mialgias	11,5	11,0	34,8	14,9
Disnea	63,5	31,0	31,2	18,7
Expectoración	ND	ND	26,8	33,7
Dolor de garganta	ND	5,0	17,4	13,9
Diarrea	ND	2,0	10,1	3,8
Náuseas/vómito	4,0	2,0	10,1	5,0
Mareo	ND	ND	9,4	ND
Cefalea	6,0	8,0	6,5	13,6
Escalofríos	ND	ND	ND	11,5
Hallazgos Radiológicos				
Infiltrados alveolares unilaterales	ND	25,0		ND
Infiltrados alveolares bilaterales	ND	75,0	100	51,8
Infiltrados intersticiales	ND	ND		14,7
Patrón de vidrio esmerilado	ND	14,0		56,4

*Serie de pacientes críticamente enfermos; ** 40% con criterios de ingreso; ND: sin datos

symptoms were: fever or recent history of fever (68.7%), cough (68.1%), sore throat (24.1%), dyspnea (31%), chills (27%), vomiting (6%), diarrhea (14%) and other respiratory symptoms (4.5%) (49). Other symptoms related to different organs and systems have also been described:

- Neurological: in a study with 214 patients admitted to a Wuhan hospital, 36% had neurological symptoms: dizziness (17%), altered level of consciousness (7%), stroke (2.8%), ataxia (0.5%) and epilepsy (0.5%), hypogeusia (5.6%), hyposmia (5%) and neuralgia (2.3%)⁽¹⁴⁾.
- Cardiological: it has been noted that sometimes the disease can present with symptoms related to heart failure or acute myocardial damage, even in the absence of fever and respiratory symptoms.⁽¹⁵⁾
- Ophthalmological: in a series of 534 patients confirmed in Wuhan, dry eye, 12.7% blurred vision, 11.8% foreign body sensation and 4.7% conjunctival congestion (0.5% presented as the first symptom)⁽¹⁶⁾.

Seven clinical series of hospitalized cases have been published in China, with 5, 41, 52, 99, 138, 1,099 and 72,314 cases respectively. The most frequent symptoms at the time of admission in all series are fever, asthenia and cough. In the series by Wang et al. fever was the most common symptom, while in Guan et al. It is noted that only 43.8% of the patients had fever at the time of admission, although during their stay in the hospital the vast majority develop it.^(17,18). Furthermore, Yang et al. refer to the fact that 11% of critically ill patients did not have fever at the onset of symptoms⁽¹⁹⁾. The most frequent radiological pattern in all series was alveolar infiltrate (see Table 1).

Table 1. Clinical characteristics of the patient series of Yang et al., Chen et al., Wang et al. and Guan et al.

2.2.3. Data reported in the oncology population

Although so far there is no evidence of the behavior of SARS-CoV-2 in the oncology population, it is possible that patients undergoing immunosuppressive oncology treatment may have a greater susceptibility to it and a higher incidence of associated complications than the general population, such as and as occurs with other respiratory viral infections such as the flu.

There is no evidence that the virus worsens the tumor pathology itself and in many cases it has a mild clinical course. However, in cancer patients it could be associated with a more severe clinical picture, the severity of which could be increased if other factors such as advanced age or the presence of other comorbidities are associated. This increased risk of complications requires strict compliance with prevention protocols and extreme caution. The recommendations made to avoid contagion to the general population must be followed particularly strictly by cancer patients.

Several overview reviews have been published (especially of Chinese and Italian experiences). The most commented article, published in Lancet Oncology a few weeks ago, reveals the possibility that cancer patients have a worse prognosis when suffering from COVID-19⁽¹⁾, but it is also true that this cohort of patients had a higher median age than for those without cancer and the proportion of patients is so small that there may be great heterogeneity in that population (cured vs. metastatic patients, etc.). To this we must add that the risk for cancer patients is also related to a greater inability to receive necessary medical care.

Despite this, recently, a new retrospective review has been published in Annals of Oncology with 28 COVID-19 + oncology patients.⁽²⁰⁾ The most common tumor in this series was lung cancer (25%), with only 3 patients with genitourinary cancer (2 patients with prostate cancer and 1 patient with testicular cancer). The median age was 65 years. The most common symptoms were fever (82.1%) and cough (78.6%), and the most common laboratory abnormalities were lymphopenia (82.1%) and elevated CRP (82.1%). The risk of severe complications was higher in patients who had received oncological treatment in the 14 days prior to the diagnosis of the infection, with an HR in the multivariate analysis adjusted for age and sex of 4.079 (95% CI 1.086-15.322, p 0.037). However, despite being the largest series collected of COVID-19+ oncology patients, it has its limitations, which are mentioned in the article itself. To begin with, this is a retrospective study of 28 patients. Furthermore, the population is heterogeneous, with different tumors and stages (64.3% are stages I-III), which is not taken into account in multivariate analysis. A more recent article in Cancer Discovery with 69 patients with lung cancer, mainly active or metastatic (80%), determined that previous oncological treatment with Programmed Dead-1 (PD-1) blockers does not have a significant impact on severity of COVID-19 infection⁽²¹⁾.

23. Working hypothesis

The identification of patients with genitourinary tumors who suffer from infection with the SARS-CoV-2 agent can represent multiple benefits both for themselves and for health professionals and the health system itself. We would be able to know more precisely the clinical evolution of this type of patient, know their prognosis and be able to select the most appropriate treatment modality for future pandemics.

3. OBJECTIVES

3.1. Main objectives

- Describe the population infected by COVID-19 with genitourinary tumors (urothelial cancer, prostate cancer, testicular cancer and renal cancer) treated in Spanish hospitals, know the clinical presentation, therapeutic evolution and prognosis of said intercurrent infectious process, as well as its possible relationship with different clinical and therapeutic factors.
- Assess the possible relationship of the different oncological treatments administered to these patients with the clinical evolution of COVID-19 infection, considering both patients who have undergone oncological treatment previously, during or after COVID-19 infection.
- To specifically evaluate the impact of COVID-19 infection on the toxicity of immunotherapy treatment (mainly pneumonitis) and the impact of immunotherapy on the evolution of the infectious condition in patients with tumors of genitourinary origin, in three different scenarios: during treatment, after treatment and in patients who are prescribed treatment after the infection has passed.
- Analysis of this same relationship in patients with genitourinary tumors and asymptomatic COVID-19 infection with positive Ab serologies (IgM and IgG).
- To evaluate in patients with Prostate Cancer (PCa) the impact of androgen deprivation therapy (ADT) and new antiandrogen agents (NAH) with or without corticosteroids on infection COVID-19.

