3.2. Secondary objectives

- To evaluate the mortality associated with COVID-19 infection in the population with genitourinary tumors. Percentage of patients alive/dead at discharge.
- To evaluate the rate (percentage) of complications that have required hospital admission and/or ICU treatment.
- Describe the frequency of asymptomatic or minimally symptomatic COVID-19 infections. Percentage of asymptomatic patients or with mild symptoms included in the study.
- Evolution of the oncological disease. Impact/influence of COVID-19 infection on the effectiveness of oncological treatment. Data will be collected on delays/modifications in follow-up or oncological treatment regimens. The average delay time and the number of modifications will be evaluated. Likewise, it is expected to obtain data on time to progression and overall survival of cancer patients, which can be compared with the reference values for each type of tumor pathology.

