4.5. Study sample size

The inclusion of a total of 250 patients with genitourinary tumors presenting with COVID-19 infection is expected, sufficient to respond to the objectives set by the study.

Given the characteristics of the study, the total number of patients cannot be previously calculated accurately, although the inclusion of approximately 250 patients is expected. The planned analysis is the descriptive one of each of the variables. The qualitative variables will be compared with each other using the Chi-square test. Quantitative and qualitative analysis using Student's T analysis or ANOVA. If necessary, the corresponding non-parametric tests will be applied. Survival will be calculated using Kaplan-Meyer curves and curve comparison using Log-Rank.

The Statistical Package for the Social Sciences (SPSS) will be used for statistical analyses. Additional analyzes could be performed with other statistical analysis packages.

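### Objectives ii and iii let cancer treatment given after the infection count as an exposure for COVID-19 outcomes, with no exposure date set; for death by discharge this can favour treatment by construction

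*Combined protocol and SAP*

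**What the plan says.** Section 3.1, repeated in the 1.2 summary, sets main objective ii as the relationship between oncological treatments and the clinical course of COVID-19, "considering both patients who have undergone oncological treatment previously, during or after COVID-19 infection". Objective iii runs in two directions: the effect of infection on immunotherapy toxicity, and "the impact of immunotherapy on the evolution of the infectious condition". Both are to be studied "in three different scenarios: during treatment, after treatment and in patients who are prescribed treatment after the infection has passed". Objective iv asks for the same relationship in asymptomatic, antibody-positive patients.

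The later-treated group can occur. Section 4.3 admits patients infected before any cancer treatment, and section 5.1 collects the date on which treatment starts or restarts after infection.

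COVID-19 mortality is a secondary objective in 3.2: "Percentage of patients alive/dead at discharge". The analysis text is in 4.5. It says "The planned analysis is the descriptive one of each of the variables", and then "The qualitative variables will be compared with each other using the Chi-square test". Kaplan-Meier curves with log-rank tests are planned for survival. No exposure window, time zero or landmark is given. Section 2.2.3 cites a series whose exposed group was "patients who had received oncological treatment in the 14 days prior to the diagnosis of the infection", so it fixed exposure before diagnosis. The objectives do not adopt such an anchor.

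**The concern.** An exposure has to precede the outcome it is related to. In objective iii's third scenario the infection is already over when immunotherapy is prescribed, so that patient has survived it. Counting such patients as exposed adds guaranteed survivors to the treated side. If they came from the untreated side, it also leaves that side with a higher proportion of deaths. This is immortal-time bias.

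At stake are part of objective ii and the half of objective iii that takes immunotherapy as the exposure. Either could show lower COVID-19 mortality with treatment when there is no effect. The other half of objective iii, infection followed by immunotherapy toxicity, has the right time order and is not in question.

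**Working it through.** **Inputs.** From the protocol: about 250 patients (4.5), death at discharge (3.2), chi-square tests (4.5). The 250 is an expected count with no calculation behind it, so there is no planned figure to reproduce. The protocol gives no mortality or treatment shares. All of the following are assumptions: mortality *m* of 10–30%, the same in everyone (no treatment effect); *u*, the share untreated at infection; *f*, the share of untreated survivors who are treated later. False-positive rates come from 20,000 simulated studies per case, two-sided 5%, with the continuity-corrected rate in brackets.

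**1. Direction for death by discharge.** Let d1 of n1 treated and d0 of n0 untreated patients die. Moving *l* later-treated survivors across gives d1/(n1 + l) against d0/(n0 − l). The death counts do not change, so the risk ratio falls with every patient moved. If later starters make up a share *k* of the treated group, its mortality reads m(1 − k): a true 20% reads 18% at k = 10% and 14% at k = 30%.

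**2. Worked example: m = 20%, u = 20%, f = 50%.**
- At infection: 200 treated with 40 deaths, 50 untreated with 10 deaths. Both are 20%.
- Of the 40 untreated survivors, 20 are treated later.
- Counted as treated: 40/220 = 18.2%. Never treated: 10/30 = 33.3%.
- False positives: 49% (41%). With exposure fixed at infection: 5% (3%).

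In general the treated group reads m(1 − u)/[(1 − u) + u(1 − m)f], and the never-treated group m/[m + (1 − m)(1 − f)].

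**3. Range.** Over u = 10–40% and f = 25–75%, false positives run from 10% (5%) at m = 10%, u = 10%, f = 25%, to 100% (100%) at m = 30%, u = 40%, f = 75%.

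**4. Immunotherapy at any timing against none, m = 20%, 10% exposed by infection.** That is 25 exposed with 5 deaths, and 225 others with 45 deaths and 180 survivors.

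| Survivors prescribed it later | Exposed | Not exposed | False positives |
|---|---|---|---|
| 5% (9 patients) | 5/34 = 14.7% | 45/216 = 20.8% | 11% (6%) |
| 20% (36 patients) | 5/61 = 8.2% | 45/189 = 23.8% | 82% (75%) |

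Over m = 10–30% and 10–20% exposed by infection, the uncorrected rate is only 3–14% when about 10 or fewer patients are prescribed it later. With exposure fixed at infection, the cases in steps 3 and 4 give 4–5% (2–4%).

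**5. Later-treated patients as their own group.** If they are a share *s* of survivors, they show 0% mortality and everyone else m/[1 − (1 − m)s]. At m = 20%, s = 10%: 0/20 against 50/230 = 21.7%, rejected in 88% (56%) of studies. At s = 5%: 0/10 against 50/240 = 20.8%, rejected in 10% (1%).

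**6. Where the direction is not fixed.**
- *One treatment against another.* Take 60 patients on each at infection, 12 deaths each, then 5 later starters on A and 40 on B: 12/65 = 18.5% against 12/100 = 12.0%, a ratio of 1.54 against A with no true difference.
- *Later all-cause death.* Take 100 treated at infection (20 deaths) and 150 others (30 COVID-19 deaths). Of the 120 survivors among those others, 40 start later and 30% of them die (12 deaths); 80 never start and 2% die (1.6 deaths). Counting late starters as treated gives (32/140)/(31.6/110) = 0.80. Exposure at infection gives (20/100)/(43.6/150) = 0.69. Here the misclassification makes treatment look worse.
- *Admission.* Assume 40% are admitted, all deaths are among them, and admitted survivors are *r* times as likely as non-admitted patients to be treated later. The difference vanishes at r = 0.4/(0.4 − m), that is 1.33, 2 or 4 for m = 10, 20 or 30%. At m = 10% with 20% of the non-admitted treated later, r = 1 gives 33.3% admitted in the later-treated group against 41.5% in the rest, and r = 2 gives 50.0% against 36.8%.

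**The case against.** The strongest reply is that the protocol does not plan the biased contrast. Section 4.5 calls the analysis descriptive and section 6.1 calls the study descriptive. Nothing pools the timing groups or names timing against death as a test. Section 4.3 uses the same three timings for eligibility, so objective ii's clause may only say which patients are covered. This stands in part: a reader might infer a planned, biased comparison, and the documents do not support that. Descriptive reporting by separate scenario would avoid the false tests. But the next sentence of 4.5 plans comparisons of the qualitative variables, the objectives speak of relationship and impact, and no exposure date limits what may be tested.

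Three other inferences go too far.
- That treatment is favoured for every outcome and contrast. Step 6 shows otherwise.
- That later-treated patients in objective ii are survivors by definition. Only objective iii says the infection has passed. Objective ii just says after infection, which could mean after diagnosis, and 5.1 records a negative test before restart as a variable and does not presume clearance.
- That the data form certainly misrecords exposure in survivors. The item on start and last dose of the latest cancer treatment has no infection anchor, but a neighbouring item on the type of latest treatment refers to the infection in unclear wording, and treatment after infection has its own item. The form is ambiguous; an error is possible but not shown.

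It is also fair to say that every size above is assumed, and that the effect may be small.

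**Conclusion.** The concern holds as an undefined exposure time for COVID-19 outcomes in objective ii and in the immunotherapy-to-infection half of objective iii. If post-infection starters are counted as treated, or tested as a timing group, death by discharge is biased in favour of treatment. For objective iii this follows from its own wording; for objective ii it requires that the infection had resolved before treatment began. For treatment-against-treatment comparisons, later all-cause survival, admission and ICU care, no direction can be claimed.

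The size cannot be known from the protocol. Under the assumptions shown, it runs from close to the nominal error rate, when few patients start later, to near-certain false significance when many do. It should be fixed, because the change is cheap and most of the needed dates are already collected.

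**What to change.** - **3.1 (ii) and (iii), and the matching text in 1.2.** Define exposure for COVID-19 outcomes as treatment status at the infection date: on treatment, previously treated, or not yet treated. Class patients first treated later as not yet treated. State the interval since last dose that separates the first two groups.
- **Infection date.** Use symptom onset where recorded, otherwise the confirmation date. For asymptomatic patients diagnosed by serology alone (objective iv), use the confirmation date, flag the timing as approximate, and add a sensitivity analysis without them.
- **Later-treatment scenario.** Keep it for immunotherapy toxicity and later oncological outcomes, with time zero at the start or restart date.
- **4.5.** State that COVID-19 outcomes will not be tested between the later-treated group and other timing groups.
- **5.1.** Make clear that both most-recent-treatment items (type, and start and last dose) mean the latest treatment before the infection, as the immunotherapy last-dose item already does.

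The cost is wording in two objectives, a sentence in 4.5 and clarification of two data items. The post-infection group no longer counts as treated in the severity analyses. Infection timing stays approximate for serology-only cases. The start or restart date is listed only under prospective follow-up, so retrospective cases without it drop out of the later-outcome analyses.
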